2.5.3 Windows for time points

Time window for MRI measurements and SDMT will be used to capture data collected between visits. It is defined in [Table 4](#) and [Table 5](#). Baseline values will be the baseline defined in the double-blind period of the study. All days in the visit window tables for double-blind period ([Table 4](#) and [Table 6](#)) and the open-label period ([Table 5](#) and [Table 7](#)) are relative to the first dose date in each period respectively.

Table 4 - Visit window for MRI variables and SDMT in the double-blind period

Week	Visit	Target day	Schedule A^a	Schedule B^b
0	Baseline	1	Up to 1st dose date	Up to 1st dose date
24	Visit 8	169	after 1 st dose date - 252	after 1 st dose date -210
36	Visit 10	253	Not applicable	211 - 294
48	Visit 12	337	253 - 420	295 - 420
72	Visit 16	505	421 - 588	421 - 588
96	Visit 20	673	589 - Last double-blind dose date + 60 days and before 1st open label dose	589 - Last double-blind dose date + 60 days and before 1st open label dose

^a SDMT and MRI variables for patients without MRI assessment for Week 36

^b MRI variables for patients with MRI assessment for Week 36

Table 5 - Visit window for MRI variables and SDMT in the open-label period

Week	Visit	Target day	SDMT	MRI variables
0	OL transition visit	1	Up to the first dose in OL period	Up to the first dose in OL period
24	OL Visit 7	169	after 1st open-label dose date - 252	Not applicable
48	OL Visit 11	337	252 - 420	after 1st open-label dose date – 504
72	OL Visit 15	505	421 – 588	Not applicable
96	OL Visit 19	673	589 – 756	505 – 840
120	OL Visit 23	841	757 – 924	Not applicable
144	OL Visit 27	1009	925 – 1092	841 – 1176
168	OL Visit 31	1177	1093 – 1260	Not applicable
192	OL Visit 35	1345	1261 - Later of the Last open-label visit date or the 1st dose date in optional additional extension period	1177 - Later of the Last open-label visit date or before 1st dose date in optional additional extension period

For multiple records within a visit window, the one closest to the targeted visit date will be used.

Selected safety variables will be summarized by the analysis window defined in [Table 6](#) and [Table 7](#) of [Section 2.5.3](#) for the by visit descriptive analysis. All available values obtained between 2 visits including unscheduled measurements will be pooled according to the visit window. In the event of multiple measurements of the same test in the same window, the one closest to the targeted visit date will be used for the by-visit summary.

Table 6 - Visit window for safety variables in the double-blind period

Week	Visit	Schedule A ^a	Schedule B ^b	Vital signs
0	Baseline	Up to 1st double-blind dose date	Up to 1st double-blind dose date	Up to 1st double-blind dose date
4	Visit 3	after 1 st double-blind dose date - 56	after 1 st double-blind dose date - 42	after 1 st double-blind dose date - 42
8	Visit 4	Not applicable	43 - 70	43 - 70
12	Visit 5	57 - 126	71 - 98	71 - 126
16	Visit 6	Not applicable	99 - 126	Not applicable
20	Visit 7	Not applicable	127 - 154	Not applicable
24	Visit 8	127 - 210	155 -189	127 - 210
30	Visit 9	Not applicable	190 - 231	Not applicable
36	Visit 10	211 - 294	232 - 273	211 - 294
42	Visit 11	Not applicable	274 - 315	Not applicable
48	Visit 12	295 - 378	316 - 357	295 - 378

Week	Visit	Schedule A ^a	Schedule B ^b	Vital signs
54	Visit 13	Not applicable	358 -399	Not applicable
60	Visit 14	379 - 462	400 - 441	379 - 462
66	Visit 15	Not applicable	442 - 483	Not applicable
72	Visit 16	463 - 546	484 - 525	463 - 546
78	Visit 17	Not applicable	526 - 567	Not applicable
84	Visit 18	547 - 630	568 - 609	547 - 630
90	Visit 19	Not applicable	610 - 651	Not applicable
96	Visit 20	631 - end of double-blind period ^c	652- end of double-blind period ^c	631 - end of double-blind period ^c

- a Schedule A includes: Coagulation panel (prothrombin time, and activated partial thromboplastin time); Complete chemistry panel (glucose, creatinine, BUN, sodium, potassium, chloride, bicarbonate, magnesium, calcium uric acid, LDH, alkaline phosphatase, inorganic phosphorus, total protein, albumin, globulin, albumin/globulin ratio, triglycerides, cholesterol and CPK. Urinalysis (pH, ketones, protein, glucose, blood, urobilinogen, bilirubin, microscopic sediment, specific gravity).
- b Schedule B includes: Hematology and differential panel (hemoglobin, hematocrit, red blood cell count, mean corpuscular hemoglobin, white blood cell count, neutrophils, lymphocytes, monocytes, eosinophils, basophils, platelets); liver function tests [ALT, AST, GGT, total bilirubin, and direct/indirect bilirubin] and pancreatic enzymes [serum amylase and lipase]).
- c End of double-blind period is defined as last double-blind dose date + 28 days and before 1st open label dose, whichever comes first.

Table 7 - Visit window for safety variables in the open-label period

Week	Visit	Schedule A ^a	Schedule B ^b	Vital signs ^d
0	OL transition visit	Up to the first dose in OL period	Up to the first dose in OL period	Up to the first dose in OL period
4	OL Visit 2	after 1 st open-label dose date - 56	after 1 st open-label dose date - 42	after 1 st open-label dose date - 42
8	OL Visit 3	Not applicable	43 - 70	43 - 70
12	OL Visit 4	57 - 126	71 - 98	71 - 126
16	OL Visit 5	Not applicable	99 - 126	Not applicable
20	OL Visit 6	Not applicable	127 - 154	Not applicable
24	OL Visit 7	127 - 210	155 -189	127 - 210
30	OL Visit 8	Not applicable	190 - 231	Not applicable
36	OL Visit 9	211 - 294	232 - 273	211 - 294
42	OL Visit 10	Not applicable	274 - 315	Not applicable
48	OL Visit 11	295 - 378	316 - 357	295 - 378
54	OL Visit 12	Not applicable	358 -399	Not applicable
60	OL Visit 13	379 – 462	400 - 441	379 - 462
66	OL Visit 14	Not applicable	442 - 483	Not applicable
72	OL Visit 15	463 - 546	484 - 525	463 - 546
78	OL Visit 16	Not applicable	526 - 567	Not applicable
84	OL Visit 17	547 - 630	568 - 609	547 - 630

Week	Visit	Schedule A ^a	Schedule B ^b	Vital signs ^d
90	OL Visit 18	Not applicable	610 - 651	Not applicable
96	OL Visit 19	631 - 714	652 - 693	631 - 714
102	OL Visit 20	Not applicable	694 - 735	Not applicable
108	OL Visit 21	715 - 798	736 - 777	715 - 798
114	OL Visit 22	Not applicable	778 - 819	Not applicable
120	OL Visit 23	799 - 882	820 - 861	799 - 882
126	OL Visit 24	Not applicable	862 - 903	Not applicable
132	OL Visit 25	883 - 966	904 - 945	883 - 964
138	OL Visit 26	Not applicable	946 - 987	Not applicable
144	OL Visit 27	967 - 1050	988 - 1029	967 - 1050
150	OL Visit 28	Not applicable	1030 - 1071	Not applicable
156	OL Visit 29	1051 - 1134	1072 - 1113	1051 - 1134
162	OL Visit 30	Not applicable	1114 - 1155	Not applicable
168	OL Visit 31	1135 - 1218	1156 - 1197	1135 - 1218
174	OL Visit 32	Not applicable	1198 - 1239	Not applicable
180	OL Visit 33	1219 - 1302	1240 - 1281	1219 - 1302
186	OL Visit 34	Not applicable	1282 - 1323	Not applicable
192	OL Visit 35	1303 - end of open-label period ^c	1324 - end of open-label period ^c	1303 - end of open-label period ^c

^a Schedule A includes: Coagulation panel (prothrombin time, and activated partial thromboplastin time); Complete chemistry panel (glucose, creatinine, BUN, sodium, potassium, chloride, bicarbonate, magnesium, calcium uric acid, LDH, alkaline phosphatase, inorganic phosphorus, total protein, albumin, globulin, albumin/globulin ratio, triglycerides, cholesterol and CPK. Urinalysis (pH, ketones, protein, glucose, blood, urobilinogen, bilirubin, microscopic sediment, specific gravity).

^b Schedule B includes: Hematology and differential panel (hemoglobin, hematocrit, red blood cell count, mean corpuscular hemoglobin, white blood cell count, neutrophils, lymphocytes, monocytes, eosinophils, basophils, platelets); liver function tests [ALT, AST, GGT, total bilirubin, and direct/indirect bilirubin] and pancreatic enzymes [serum amylase and lipase]).

^c End of open-label period is defined as later of the last open-label visit date or before 1st dose date in the optional additional extension period.

^d If remote visits, only weight will be collected for vital signs. Assessment date should be collected separately for weight and other assessments.

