EOT = end of treatment (EOT= First visit after last study drug intake), EDSS = expanded disability status scale, FS = functional score, BVMTR = brief visuospatial memory test-revised, SDMT=symbol digit modalities test, MRI = magnetic resonance imaging, PK = pharmacokinetic

- a Recommended windows: The window for obtaining biological samples at any given visit will be ±7 days. All other treatment period assessments should be completed within ±7 days of the scheduled visit date relative to the randomization visit. Post drug elimination follow-up visits should be ±7 days of scheduled visit relative to end of treatment.
- b Randomization visit up to 28 days from signing of informed consent.
- c End-of-treatment and premature discontinuation visit. This visit does not need to be performed when the patient switches to the open label period after a confirmed relapse or high MRI activity (as per protocol criteria). The drug elimination procedure must be initiated at this visit if applicable.

- d* For discontinuing treatment, 2 post drug elimination follow up visits should be scheduled 2 weeks and 4 weeks after study medication discontinuation and initiation of the drug elimination procedure. All patients who prematurely and permanently discontinue study medication will be asked to continue until the planned end of double-blind period.
- e* Re-consent must follow any RAP confirmed MS relapse for continuing in study when occurrence during PK run-in, for switching into open-label period when occurrence after PK run-in.
- f* To be prescribed at Visit 1 and report checked at Visit 2. MRI scan performed within 6 weeks prior to randomization can be used as the baseline MRI if performed according to the operations manual and accepted by the central reader.
- g* During the adverse event reporting process, specific questions about pulmonary symptoms and peripheral neuropathy symptoms will be asked. (Patients will be instructed to alert the treating physician of symptoms suggestive of immunodeficiency).

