- a The open label period starts by the transition visit. It is recommended that there is no time gap between the 2 periods, or as short as possible and if possible less than 2 weeks. In case of start of the open label period at the end of the 96 weeks of the double-blind period, the transition visit will generally coincide with the EOT visit of the double-blind period. Recommended windows: The window for obtaining biological samples at any given visit will be  $\pm 7$  days. All other treatment period assessments should be completed within  $\pm 7$  days of the scheduled visit date relative to the transition visit. Post drug elimination follow-up visits should be  $\pm 7$  days of scheduled visit relative to end of treatment.
- b For a regional or national emergency declared by a governmental agency, contingency measures are included in [Section 17.7](#)
- c End-of-treatment and premature discontinuation visit.
- d For patients discontinuing treatment, 2 post drug elimination follow up visits should be scheduled 2 weeks and 4 weeks after study medication discontinuation and initiation of the drug elimination procedure. When applicable patients who prematurely and permanently discontinue study medication will be asked to continue until the planned end of double-blind period (ie, 96 weeks after randomization)
- e Re-consent before starting open-label period and after confirmed MS relapse and when patients turn adults as per local regulations.
- f During the adverse event reporting process, specific questions about pulmonary symptoms and peripheral neuropathy symptoms will be asked. (Patients will be instructed to alert the treating physician of symptoms suggestive of immunodeficiency)
- g Including systolic and diastolic blood pressure, heart rate, body temperature, weight and height; patient standing in bare or stocking feet. Height and weight is to be documented in the growth charts –Blood pressure (BP) and heart rate to be measured in both the supine and the standing positions (measures taken 3 minutes after supine and 3 minutes after standing). A sphygmomanometer with a blood pressure cuff appropriate to the patient's arm girth is used. Of note, during remote visits, only weight will be collected.
- h Tanner stage to be assessed at every 24 weeks and EOT for all patients (until complete sexual maturity).

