### 10.1 VISIT SCHEDULE

It is preferred that all study visits take place in the morning. Visits can be performed on 2 consecutive days when convenient. If a patient is prematurely discontinued from the study treatment, all EOT visit procedures should be performed.

The visit schedule consists of the following visits:

- Screening (Visit 1/Week -4) up to 4 weeks prior to the randomization visit (Visit 2).
  - No IMP is administered in this period.
- Double-Blind Treatment period
  - Randomization (to either teriflunomide or placebo) at randomization (Visit 2),
  - Patients will be on the treatment period of the study for 96 weeks unless prematurely discontinued or switching to the open-label extension period,
  - Patients experiencing a relapse after the PK run-in period (8 weeks) and if confirmed by the Relapse Adjudication Panel (RAP) will have the option to continue in an open label teriflunomide treatment arm. If RAP does not confirm the relapse, the patient may continue in the double-blind treatment period or prematurely discontinue treatment,
  - Visit 3 (W4) to Visit 20 (W96/EOT),
  - For patients prematurely discontinued from treatment, Visit 20 (W96/EOT) procedures should be performed,
  - Clinical laboratories are performed in both routine study site visits and safety laboratory visits that are performed locally (see [Section 1.2](#); two separate lines in the flowchart to indicate the different schedules),
  - In case of at least 5 new/enlarged T2 lesions at the MRI of Week 24, an additional MRI will be performed at Week 36. Then, in case of -at least 9 new/enlarged T2 lesions at Week 36 or -at least 5 new/enlarged T2 lesions on each of the 2 consecutive MRI scans of Week 36 and Week 48, or at least 5 new/enlarged T2 lesions on each of the 2 consecutive MRI scans of Week 48 and Week 72, patients will have the option to continue in the open label period.
- Post drug elimination follow up period (4 weeks)
  - No IMP is administered in this period,
  - Patients who complete the treatment period as well as patients who discontinue prematurely should be scheduled for 2 follow-up visits (Visit 21 and Visit 22),

- Patients will be taking non-IMP (either cholestyramine or activated charcoal) to accelerate the drug elimination process, starting immediately after IMP discontinuation (ie, the same day or the day after).

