2.4.4.2.3 Magnetic resonance imaging (MRI) variables

General rules for MRI variables

The protocol requires that the MRI should not be performed until after a minimum of 14 days following completion of corticosteroid therapy. Thus, MRI values obtained within 14 days of systemic corticosteroid therapy will be excluded from the analysis.

Baseline for MRI variables is defined as the last non-missing, valid MRI value that was measured before or on the day of first administration of IMP in the double-blind period. A previous MRI performed in the 6 weeks preceding randomization could be used as the baseline if performed according to the specifications for this study. For valid MRI values in subsequent post baseline visits, time windows (see [Table 4](#) and [Table 5](#) in [Section 2.5.3](#)) between visits will be used to capture MRI measurements. For multiple records within a visit window, the one closest to the targeted visit date will be used.

Number of lesions

The number of new or enlarged T2 lesions per MRI scan will be analyzed using a negative binomial regression model with robust variance estimation. The model will include the total number of new or enlarged T2 lesions as the response variable, with treatment group, region, pubertal status and age as covariates. In order to account for different numbers of MRI scans performed among patients, the log-transformed number of scans will be included in the model as an offset variable. The robust error variances can be estimated by specifying the patient identifier in the repeated statement using SAS PROC GENMOD. The estimated number of lesions per scan and associated 2-sided 95% confidence interval (CI) will be provided for each treatment group.

The number of T1 Gd-enhancing lesions per MRI scan and the number of new T1 hypointense lesions per MRI scan will be analyzed using a similar negative binomial regression model as described above for T2 lesions.

Volume of lesions and brain

Descriptive statistics of the change from baseline in volume of T2 lesions, T1 hypointense lesions and the percentage change of brain volume in the original scale will be summarized at each visit by treatment group.

The proportion of patients free of new or enlarged T2 lesions

The proportion of patients free of new or enlarged T2 lesions at Weeks 48, 96, 144 and 192 will be summarized based on all patients having an MRI at these time points. Kaplan-Meier methods will be used for estimation.

Censoring rule

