Week (W) ^a	W102	W108	W114	W120	W126	W132	W138	W144	W150	W156	W162	W168	W174	W180	W186	W192/ EOT ^{b, u}	EOT +2W	EOT +4W	Relapse visit
Visit number ^r	20	21	22	23	24	25	26	27	28	29	30	31	32	33	34	35	36 ^c	37 ^c	
Treatments																			
Concomitant medications	X	X	X	X	X	X	X	X	X	X	X	X	X	X	X	X	X	X	X
Dispense study drugs/IVRS call		X		X		X		X		X		X		X		X ^t			
Accountability/co compliance		X		X		X		X		X		X		X		X			
Teriflunomide PK sampling ^k																X	X ^l	X ^l	

EOT = end of treatment (EOT= First visit after last study drug intake), EDSS = expanded disability status scale, FS = functional score, BVMTR = brief visuospatial memory test-revised, SDMT=symbol digit modalities test, MRI = magnetic resonance imaging, PK = pharmacokinetic.

- a The open label period starts by the transition visit. It is recommended that there is no time gap between the 2 periods, or as short as possible and if possible less than 2 weeks. In case of start of the open label period at the end of the 96 weeks of the double-blind period, the transition visit will generally coincide with the EOT visit of the double-blind period. Recommended windows: The window for obtaining biological samples at any given visit will be ±7 days. All other treatment period assessments should be completed within ±7 days of the scheduled visit date relative to the transition visit. Post drug elimination follow-up visits should be ±7 days of scheduled visit relative to end of treatment.
- b End-of-treatment and premature discontinuation visit.
- c For patients discontinuing treatment, 2 post drug elimination follow up visits should be scheduled 2 weeks and 4 weeks after study medication discontinuation and initiation of the drug elimination procedure. When applicable patients who prematurely and permanently discontinue study medication will be asked to continue until the planned end of double-blind period (ie, 96 weeks after randomization).
- d Re-consent before starting open-label period and after confirmed MS relapse and when patients turn adults as per local regulations.
- e During the adverse event reporting process, specific questions about pulmonary symptoms and peripheral neuropathy symptoms will be asked. (Patients will be instructed to alert the treating physician of symptoms suggestive of immunodeficiency).

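### SAP 2.5.3: a protocol-compliant Week 96 MRI or SDMT done after the first open-label dose is dropped, or tabulated as open-label Week 48 (MRI) or Week 24 (SDMT)

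*SAP*

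**What the plan says.** SAP 2.5.3, Table 4 gives the double-blind Week 96 window for MRI and SDMT as "589 - Last double-blind dose date + 60 days and before 1st open label dose", with target day 673. In Table 5 the open-label Week 48 MRI window is "after 1st open-label dose date – 504" (target day 337). The open-label Week 24 SDMT window also starts after that dose date and ends on day 252 (target day 169). Days in these tables "are relative to the first dose date in each period respectively".

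On choosing between records, SAP 2.4.4.2.3 says: "For multiple records within a visit window, the one closest to the targeted visit date will be used". That section names Tables 4 and 5 as the windows for its MRI variables. SAP 2.5.4 assigns unscheduled MRI and SDMT by the same windows, and nothing lets the recorded visit override the date.

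On timing, Protocol 1.2 (footnote a) says: "All other treatment period assessments should be completed within ±7 days of the scheduled visit date relative to the randomization visit". Protocol 10.1 adds: "Visits can be performed on 2 consecutive days when convenient". On the move into open label, Protocol 1.4 (footnote a) says: "It is recommended that there is no time gap between the 2 periods". For patients who finish 96 weeks, SAP Appendix C says "the transition visit will generally coincide with the EOT visit of the double-blind period". The Protocol 1.3 flow chart has open-label drug dispensed at the transition visit.

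**The concern.** Each rule is reasonable alone, but they do not fit together. The protocol tolerates a Week 96 assessment up to a week late, encourages immediate rollover, and nowhere requires the Week 96 MRI or SDMT to come before the first open-label dose. The SAP uses that dose as a hard boundary. A compliant but slightly late assessment crosses it and is treated as an early open-label record, far from any open-label target day.

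Two outcomes are possible. If the true open-label Week 48 scan (or Week 24 SDMT) exists, it is closer to target and the Week 96 record is not used. If it is missing, the Week 96 record stands in for it. The note in Protocol 8.1 counts new or enlarged lesions against the previous scan. If the endpoint counts follow that convention, dropping the scan removes Week 72-96 activity from the lesion totals. Relabelling it shows activity accrued on placebo as open-label Week 48 in the placebo/teriflunomide group. The T2 and Gd-enhancing lesion counts are the key secondary imaging endpoints in SAP 2.1.3.2.

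**Working it through.** **Reproducing the tables.** Target day = 7 × week + 1:
- Week 24: 169
- Week 48: 337
- Week 72: 505
- Week 96: 673

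Each window opens at the midpoint of adjacent targets:
- Double-blind Week 96: (505 + 673)/2 = 589, as in Table 4.
- Open-label Week 96 MRI: (337 + 673)/2 = 505, which agrees with Week 48 ending on day 504.

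**Compliant Week 96 days.** 673 ± 7 gives days 666-680, which is 15 days. This takes the first double-blind dose as given on the randomization day.

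**Assigning the days.** Let F be the double-blind day of the first open-label dose, with no gap between periods. An assessment on day d > F is outside Table 4 Week 96 and falls on open-label day d − F + 1. The number of compliant days after F is 680 − F.

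| F | Compliant days after F | Latest open-label day |
|---|---|---|
| 666 | 14 of 15 | 15 |
| 673 | 7 of 15 (days 674-680) | 8 |
| 680 | 0 of 15 | none after the dose date |

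**Where they land.** Open-label days 2-15 lie inside the Week 48 MRI window (up to 504) and the Week 24 SDMT window (up to 252). The distance to target is 337 − 15 = 322 to 337 − 2 = 335 days for MRI, and 169 − 15 = 154 to 169 − 2 = 167 days for SDMT. A real open-label visit within ±7 days of schedule is always closer, so it displaces the Week 96 record. Without that visit, the Week 96 record is the only candidate.

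**The 60-day allowance.** In Table 4 it has no effect for patients who roll over without a gap, because the first open-label dose comes first.

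**Same-day results.** Both later windows start after the first open-label dose date, so a same-day result cannot reach Week 48 or Week 24. Compared by date, it goes at worst to open-label Week 0. The tables count whole days. Only if clock times were compared would a result taken after the dose on the same day fit neither row.

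**Two wrong limits in the same section.**
- SDMT: the Week 24/48 boundary is (169 + 337)/2 = 253. Table 5 starts Week 48 at 252 while Week 24 ends at 252, so day 252 is in two windows.
- Vital signs: the Week 132 target is 7 × 132 + 1 = 925 and the Week 144 target is 1009, with midpoint 967. Table 7 starts Week 144 at 967 but ends Week 132 at 964, so days 965-966 are in no window. Schedule A in the same table ends Week 132 at 966.

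**The case against.** The strongest reply is that the boundary is coherent. Ending double-blind data at the first open-label dose keeps results on teriflunomide out of the placebo period, and Table 6 uses a similar cut for safety. That may be the intent. However, the SAP does not say so, and it leaves the compliant late result to be discarded or relabelled. Its Covid-19 rules for delayed assessments cover only those scheduled in the open-label period.

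The second reply is low stakes. SAP 2.4.4 calls the open-label efficacy analyses exploratory. Lesion volumes, brain volume and SDMT are summarised descriptively, and the lesion-free Kaplan-Meier analysis censors by scan date, not by visit label. All of that stands. What remains exposed is the by-visit summaries and the lesion counts. SDMT is less exposed than MRI, because it is scheduled at the Week 96/EOT visit itself and would slip mainly when a visit is split over two days.

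Four stronger readings are tempting but not supported:
- *The double-blind results are damaged.* SAP section 2 says the double-blind analysis has its own SAP, which was not supplied, so nothing follows for it.
- *7 of 15 days means 47% of patients.* That is a share of calendar days for dosing exactly on day 673. It ranges from 14 of 15 to 0 of 15 as the visit moves, and the documents give no distribution of assessment dates.
- *The open-label end was given a general allowance that the double-blind end lacks.* The SAP change table ties the modified open-label EOT window to possible Covid-19 delay.
- *Both wrong limits are left over from the one-day correction in the change table.* 252 fits (253 − 1). 964 does not, because the uncorrected limit would be 965.

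**Conclusion.** The point holds for the open-label report. As written, Tables 4 and 5 misassign or drop a protocol-compliant Week 96 MRI or SDMT done after the first open-label dose, and no other rule recovers it. It applies only to patients who complete 96 weeks, enter open label without a gap, and have the assessment after that dose. Patients who switch early for a confirmed relapse or high MRI activity need no double-blind EOT visit and are outside it. The number affected cannot be derived from the documents.

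The effect is on exploratory summaries and lesion counts, not on a confirmatory test. The two wrong limits are plain errors that do not depend on this argument. A modest SAP correction is justified, because stated rules would otherwise discard or mislabel valid data.

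**What to change.** **Table 4, Week 96 row (MRI and SDMT).** Assign the assessment recorded as the double-blind Week 96/EOT visit to double-blind Week 96, including on the day of or after the first open-label dose, if it lies within the protocol's ±7 days for Week 96. Flag those done after the first open-label dose. Align the rule with the double-blind SAP, so that the two reports show the same Week 96 values.

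**Table 5.** Exclude that assessment from the open-label Week 48 MRI and Week 24 SDMT windows.

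A fixed allowance of 7 days after the first open-label dose would not do the same job: with dosing on day 666, compliant assessments run to open-label day 15.

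**Limits.** Change the SDMT open-label Week 48 start from 252 to 253, and the vital signs open-label Week 132 end from 964 to 966.

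**Cost.** SAP wording and window programming only. The downside is that a few assessments labelled double-blind will follow some days of open-label drug. The flag makes them visible and allows a summary without them. Scans delayed beyond ±7 days, for example by the 14-day wait after steroids, remain outside this rule.
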